7.1.9.7 Local Regional Control

Time to locoregional failure is defined as the time from the date of randomization to the date of the first record of appearance of local or regional progression/recurrence, to the date of neck dissection \leq 20 weeks performed for clinical or radiological (RECIST 1.1) disease progression from end of CRT when invasive cancer is present, to the date of neck dissection $>$ 20 weeks from end of CRT when invasive cancer is present, or to the date of salvage surgery of primary tumor when invasive cancer is present performed for clinical or radiological (RECIST 1.1) disease progression, whichever comes first. When neck dissection or salvage surgery of the primary tumor site is indicated but not possible, date of locoregional failure can be defined as the date of biopsy that confirms presence of invasive cancer.

Distant recurrence/progression diagnosed before locoregional failure and death in absence of locoregional failure are not considered events of interest, but as competing risks events in the analysis of this endpoint.

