7.1.10.2 Local Failure

Local failure will be primarily determined by evidence of progression or recurrence clinically or radiologically. For clinical and radiographic assessments, RECIST 1.1 criteria for progressive disease shall be used whenever applicable (see Section 7.1.9). In the case of nonmeasurable disease or in circumstances where laryngeal oedema complicates the interpretation of radiological measurements, unequivocal clinical description of disease progression is required. Biopsy proof of progressive disease is desirable but is not essential if progression documented. Any form of salvage surgery at the primary site after 12 weeks post CRT will be considered either local or regional progression unless the pathology shows no evidence of disease. If a subject has a biopsy result showing disease at the primary site at the time of or beyond 12 weeks after completion of CRT, this can be used as evidence for local failure, even if no other evidence of progression has been documented.

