7.1.10.4 Locoregional Failure

This is defined as local failure, regional failure, or both. For the purposes of determining site of first failure, the category of both will be applicable if local and regional failure occurs within one month of each other.

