8.4 Analysis Endpoints

8.4.1 Efficacy Endpoints

8.4.1.1 Primary: Event-Free Survival (EFS)

Event-free survival (EFS) is defined as the time from the date of randomization to the date of first record of any of the following events:

Progression per RECIST 1.1 by BICR or biopsy as indicated for:

- Locoregional progression or recurrence
- Distant metastasis

Surgery:

- Salvage surgery for persistent or residual disease at the primary tumor site requiring surgical removal when invasive cancer is present on final pathology
 - If salvage surgery of the primary tumor site cannot be performed, biopsy completed 12 or more weeks following completion of CRT is an event if invasive cancer is present.
- Neck dissection or surgery (performed for clinical or radiological disease progression per RECIST 1.1) \leq 20 weeks from end of CRT when invasive cancer is present

- Neck dissection or surgery >20 weeks from end of CRT when invasive cancer is present
 - If neck dissection or surgery cannot be performed, biopsy completed 12 or more weeks following completion of CRT is an event if invasive cancer is present.

Death due to any cause.

The criteria for an EFS event are comprehensively defined in Section 7.1.4.3. See Section 8.6.1 for the censoring rules.

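### The exploratory local regional control endpoint counts primary-site salvage surgery only when done for progression, which conflicts with the local failure, event and EFS rules and allows two scorings of resected residual cancer

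*Combined protocol and SAP*

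**What the plan says.** Section 7.1.9.7 (Local Regional Control) defines time to locoregional failure through several limbs, of which the earliest counts. The general limb runs to "the date of the first record of appearance of local or regional progression/recurrence". The salvage limb runs "to the date of salvage surgery of primary tumor when invasive cancer is present performed for clinical or radiological (RECIST 1.1) disease progression". The words "When neck dissection or salvage surgery of the primary tumor site is indicated but not possible, date of locoregional failure can be defined as" introduce a biopsy fallback, which takes the day of the biopsy that shows invasive cancer. The competing events are limited to two: "Distant recurrence/progression diagnosed before locoregional failure and death in absence of locoregional failure are not considered events of interest".

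Section 7.1.10.2 (Local Failure) attaches no reason-for-surgery condition: "Any form of salvage surgery at the primary site after 12 weeks post CRT will be considered either local or regional progression", with the single exception of pathology that shows no disease. On a positive primary-site biopsy at or beyond 12 weeks after CRT, it says "this can be used as evidence for local failure, even if no other evidence of progression has been documented". Section 7.1.10.4 then gives locoregional failure its own definition: "This is defined as local failure, regional failure, or both".

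The EFS definition, worded identically in 7.1.9.6 and 8.4.1.1, lists as an event "Salvage surgery for persistent or residual disease at the primary tumor site requiring surgical removal when invasive cancer is present on final pathology". Section 7.1.4.3 treats salvage surgery at the primary site with invasive cancer as local treatment failure whenever it is done. Table 16, scenarios 1 and 5, scores it as an event whether or not there is radiographic progression by BICR.

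**The concern.** Sections 7.1.9.7 and 7.1.10.4 both say what locoregional failure is, and they differ for a situation that the protocol itself plans for. Under Section 5.3, a primary site that is PET-positive 12 weeks after CRT leads to endoscopy and biopsy, and then to salvage surgery if the subject is fit and accepts it. Section 7.1.4.3 bases that management on the PET response. RECIST progression is not required, so surgery for residual disease without progression is a foreseeable case.

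At stake is the event count for local regional control, listed as an exploratory comparison in Section 3.3. If the progression condition is applied literally, a subject whose primary tumor was not eradicated by CRT stays in the risk set as locoregionally controlled. Later events may not correct this. The same surgery is an EFS event. Under Section 7.1.8.3.3.1 protocol imaging runs only until an event, and under 7.1.8.3.4 the subject then passes to survival follow-up by telephone or record review. Section 7.1.1.8 collects standard-of-care images in that phase only for subjects who have not yet had an event. A later local recurrence could therefore go unrecorded, and a later death could enter as a competing event.

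**Working it through.** This is a question of definition. The plan gives no figure to reproduce, and no formula applies. The check takes one subject through each rule.

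Test case: primary site PET-positive 12 weeks after CRT; no clinical or RECIST progression; positive biopsy at 12 weeks or later; then either (A) salvage resection more than 12 weeks after CRT with invasive cancer in the specimen, or (B) surgery indicated but not possible.

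| Rule | A: resected | B: surgery not possible |
|---|---|---|
| EFS, 7.1.9.6 and 8.4.1.1 | Event | Event |
| 7.1.4.3, Table 16 | Event (scenario 1) | Event (scenario 2) |
| 7.1.10.2 with 7.1.10.4 | Locoregional failure | Locoregional failure, by the biopsy rule |
| 7.1.9.7, plain wording | Neither event nor competing event | Failure at biopsy date |
| 7.1.9.7, general limb read through 7.1.10.2 | Event | Failure at biopsy date |

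The fourth row, column A, follows in four steps.

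1. The salvage limb is not met, because the surgery was for residual disease and not for progression.
2. The general limb speaks of progression or recurrence appearing. It does not name residual or persistent disease, which the EFS rule names separately.
3. The biopsy fallback does not apply, because it is confined to surgery that is not possible.
4. Surgery for residual disease is not among the listed competing events.

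Column B of that row is a failure because the fallback carries no progression condition. On the plain wording, then, two subjects with the same PET result and the same biopsy are scored differently according to operability alone.

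Nothing suggests that this difference is intended. For the neck, Section 7.1.10.3 gives a reason for not counting residual nodes completely resected within 20 weeks without progression: the dissection belongs to the planned treatment. No such reason is given for the primary site, where 7.1.4.3 and 7.1.10.2 go the other way.

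There is also a smaller mismatch in timing. Section 7.1.10.2 speaks only of salvage surgery after 12 weeks and is silent on earlier surgery, whereas 7.1.4.3 has no time limit.

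**The case against.** The strongest reply is that the definition should be read as a whole. Section 7.1.10.2 says that salvage surgery after 12 weeks is to be considered local or regional progression, which is almost the language of the general limb of 7.1.9.7. On that reading, case A is an event through the general limb, whatever the salvage limb says. The biopsy may bring it in even earlier: Section 5.3.1 requires histology before a primary-site salvage resection, 7.1.10.2 accepts a positive biopsy from 12 weeks as evidence of local failure, and 7.1.9.5 dates an event from pathological confirmation of progressive or residual cancer. Section 5.10.1 also describes salvage for residual disease as done for clinical progression, so the protocol does not keep the terms strictly apart. Finally, Section 8.6.1 leaves exploratory methods to the sSAP, which is not among the documents and may settle the derivation.

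Much of this stands. The integrated reading is possible, and for that reason the literal scoring cannot be presented as what the analysis did. But that reading leaves the progression qualifier in the salvage limb with almost no work to do after 12 weeks, and a programmer following 7.1.9.7 as written would not reach it. The reply shows that the text supports two scorings. It does not show that the text is clear.

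It is also fair to say that EFS is a different endpoint and need not match. The conflict that matters most is between 7.1.9.7 and 7.1.10.2 with 7.1.10.4, because these define the same term.

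**Conclusion.** The conflict is real and should be resolved. The progression condition on primary-site salvage surgery in 7.1.9.7 is at odds with 7.1.10.2 and 7.1.10.4, with 7.1.4.3, and with the EFS rule. It leaves one kind of subject, with residual primary cancer resected without progression, open to two scorings.

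A reader might infer more than this, and the documents do not support it:

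- **Local regional control is overstated.** This holds only on the plain wording. On the integrated reading these subjects are counted, and the documents do not show which was used.
- **A particular number of failures is missed.** The documents give no rate of residual-disease salvage surgery, so no number can be derived. Nor can any effect on the difference between arms, which would depend on how such surgeries fall between the arms.
- **This is the main route to primary-site failure.** The protocol plans the route but does not rank it against others.
- **The confirmatory results are affected.** They are not. EFS counts this surgery under its own rule, OS does not depend on it, and local regional control has no share of alpha, power or sample size.

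The conclusion rests on the wording alone and would be narrowed if the sSAP states the derivation.

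**What to change.** Reword the salvage limb of 7.1.9.7 so that, as in 8.4.1.1, primary-site salvage surgery with invasive cancer in the specimen counts when done for persistent or residual disease as well as for progression. Reconcile the timing in 7.1.10.2 (after 12 weeks) with 7.1.4.3 (no time limit). These are endpoint-definition edits and change nothing in how subjects are managed.

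The edits are short, and the surgery and pathology data already feed EFS, so no new collection is needed. They are not quite free, however. Section 7.1.4.2 records that the final efficacy analysis is complete. Section 8.0 allows exploratory changes to be documented in the sSAP only before any analysis is conducted, and requires post hoc exploratory work to be identified in the CSR. The sponsor should therefore document which rule was applied to local regional control. If it was the narrow one, report the endpoint under the aligned rule as well, identified as post hoc, with the number of subjects per arm whose status changes. That costs one re-derivation of an exploratory endpoint. If the broader rule was applied, a sentence saying so is enough for the analysis.

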7.1.9.8 Distant Metastasis Free Survival

Distant metastasis free survival is defined as the time from the date of randomization to the date of first record of appearance of distant metastasis or death for any cause. Locoregional failure or second cancers diagnosed before the distant metastases are not considered events of interest for this endpoint.

7.1.9.9 Overall Survival

Overall survival (OS) is defined as the time from the date of randomization to the date of death for any cause.

7.1.10 Assessment of Response

7.1.10.1 Measurement of Response

Due to the difficulties in objectively assessing response following chemoradiation, response will not be a study endpoint, but measurements will be recorded to assist with determination of progressive disease and locoregional failure status. Measurements will be taken from CT or MRI and the same method should be used to follow subjects unless medically contraindicated. All subjects will have a clinical and radiological (CT or MRI and FDG-PET or FDG-PET/CT) assessment at Week 20 (12 weeks post-completion of CRT) as defined in Section 7.1.4.

7.1.10.2 Local Failure

Local failure will be primarily determined by evidence of progression or recurrence clinically or radiologically. For clinical and radiographic assessments, RECIST 1.1 criteria for progressive disease shall be used whenever applicable (see Section 7.1.9). In the case of nonmeasurable disease or in circumstances where laryngeal oedema complicates the interpretation of radiological measurements, unequivocal clinical description of disease progression is required. Biopsy proof of progressive disease is desirable but is not essential if progression documented. Any form of salvage surgery at the primary site after 12 weeks post CRT will be considered either local or regional progression unless the pathology shows no evidence of disease. If a subject has a biopsy result showing disease at the primary site at the time of or beyond 12 weeks after completion of CRT, this can be used as evidence for local failure, even if no other evidence of progression has been documented.

7.1.10.3 Regional Failure

If neck disease cannot be completely resected at neck dissection, this will be deemed to be regional failure. If they have completely resected positive nodes from a neck dissection performed in the absence of clinical or radiographic progression ≤ 20 weeks after completion of CRT, they will not be considered to have experienced regional progression since the neck dissection completed within this timeframe is part of the pre-determined treatment package.

Subjects who do not have a neck dissection because their neck disease is judged to be unresectable will only be deemed to have failure in the neck after biopsy or cytological confirmation is obtained or disease progression is documented. Regardless of the neck

management chosen, if he/she undergoes salvage neck dissection at any time based on clinical or radiographic findings of progressive disease, then the subject meets the criteria for regional failure provided the pathology report confirms the presence of cancer.

Development of any new positive nodes not present at baseline or recurring/progressing nodes will be considered evidence of regional progression.

7.1.10.4 Locoregional Failure

This is defined as local failure, regional failure, or both. For the purposes of determining site of first failure, the category of both will be applicable if local and regional failure occurs within one month of each other.

7.1.10.5 Distant Failure

This is defined as the presence of positive pathological or radiological evidence of recurrent disease at any site of the body with the exception of those defined as 'local' or 'regional'.

When distant metastases are the first indication of relapse, then the subject must be examined for locoregional disease.

7.1.11 Post-CRT Neck Surgery

7.1.11.1 Neck Dissection

Participating centres will be required to adhere to the following policies regarding post-CRT neck dissection in subjects who have achieved a complete response at the primary site.

No neck surgery may be performed before the post-CRT assessment in Week 20 from randomization (12 weeks following completion of CRT) unless there is evidence of progressive disease. Subjects who achieve a complete clinical and complete metabolic response as assessed by FDG-PET or FDG-PET/CT in Week 12 post-completion of RT **will not** have any neck dissection. Those subjects with a residual nodal mass and evidence of metabolic activity on FDG-PET or FDG-PET/CT at that time should proceed immediately to neck dissection. Any residual metabolically inactive mass may be observed for continued regression with the FDG-PET or FDG-PET/CT being repeated at 3 monthly intervals up to 9 months post-CRT or follow local institutional guidelines. If the nodal mass ceases regressing or begins to grow and/or a subsequent FDG-PET or FDG-PET/CT scan shows metabolic activity the subject **must** proceed to neck dissection. If the subject has a residual nodal mass with short axis >1 cm but <2 cm at 9 months post-CRT that remains static in size and FDG-PET or FDG-PET/CT negative, it may be continued to be observed.

The extent of neck dissection may be selective or comprehensive according to the initial extent of nodal disease. In subjects with limited nodal disease pre-treatment, a selective neck dissection is preferred.

7.1.11.2 Salvage Neck Dissection

Salvage neck dissection for recurrent disease (after achieving a complete response in the neck) may be undertaken at any time according to clinical indications.

7.2 Assessing and Recording Adverse Events

An adverse event is defined as any untoward medical occurrence in a patient or clinical investigation subject administered a pharmaceutical product and which does not necessarily have to have a causal relationship with this treatment. An adverse event can therefore be any unfavourable and unintended sign (including an abnormal laboratory finding, for example), symptom, or disease temporally associated with the use of a medicinal product or protocol-specified procedure, whether or not considered related to the medicinal product or protocol-specified procedure. Any worsening (i.e., any clinically significant adverse change in frequency and/or intensity) of a preexisting condition that is temporally associated with the use of the Sponsor's product, is also an adverse event.

Changes resulting from normal growth and development that do not vary significantly in frequency or severity from expected levels are not to be considered adverse events. Examples of this may include, but are not limited to, teething, typical crying in infants and children and onset of menses or menopause occurring at a physiologically appropriate time.

Sponsor's product includes any pharmaceutical product, biological product, device, diagnostic agent or protocol-specified procedure, whether investigational (including placebo or active comparator medication) or marketed, manufactured by, licensed by, provided by or distributed by the Sponsor for human use.

Adverse events may occur during clinical trials, or as prescribed in clinical practice, from overdose (whether accidental or intentional), from abuse and from withdrawal.

Progression of the cancer under study is not considered an adverse event.

All adverse events that occur after the consent form is signed but before treatment allocation/randomization must be reported by the investigator if they cause the subject to be excluded from the trial, or are the result of a protocol-specified intervention, including but not limited to washout or discontinuation of usual therapy, diet, placebo treatment or a procedure. From the time of treatment allocation/randomization through 30 days following cessation of treatment, all adverse events must be reported by the investigator. Such events will be recorded at each examination on the Adverse Event case report forms/worksheets.

All adverse events considered to be post-surgical complications by the investigator from time of protocol-specified surgery through 30 days following surgery, must be reported by the investigator.

The reporting timeframe for adverse events meeting any serious criteria is described in section 7.2.4.1. The investigator will make every attempt to follow all subjects with non-serious adverse events for outcome.

Electronic reporting procedures can be found in the Electronic Data Capture (EDC) data entry guidelines. Paper reporting procedures can be found in the Investigator Trial File Binder (or equivalent).

7.2.1 Definitions of Medication Error, Misuse, and Abuse

Investigators need to document if an SAE is associated with a medication error, misuse, or abuse.

Medication Error

This is an unintended failure in the drug treatment process that leads to or has the potential to lead to harm to the participant.

Misuse

This refers to situations where the medicinal product is intentionally and inappropriately used not in accordance with the terms of the product information.

Abuse

This corresponds to the persistent or sporadic, intentional excessive use of a medicinal product for a perceived psychological or physiological reward or desired non-therapeutic effect.

7.2.2 Definition of an Overdose for This Protocol and Reporting of Overdose to the Sponsor

For this trial, an overdose will be defined as ≥ 1000 mg (5 times the dose) of pembrolizumab and as any dose $\geq 20\%$ over the prescribed dose for the CRT treatments. No specific information is available on the treatment of an overdose of pembrolizumab. In the event of overdose, the subject should be observed closely for signs of toxicity. Appropriate supportive treatment should be provided if clinically indicated.

Cisplatin Overdose

There is no specific antidote for cisplatin overdose. Overdose may result in the side effects associated with the drug occurring in an excessive manner.

Otherwise, overdose should be managed according to local label and practice.

Radiation Overdose

There is no specific antidote for radiation overdose. In the event of an overdose, the subject should be observed closely for signs of toxicity. Appropriate supportive treatment should be provided if clinically indicated.

Reporting of Overdose to the Sponsor

If an adverse event(s) is associated with (“results from”) the overdose of Sponsor's product or vaccine, the adverse event(s) is reported as a serious adverse event, even if no other seriousness criteria are met.

If a dose of Sponsor's product or vaccine meeting the protocol definition of overdose is taken without any associated clinical symptoms or abnormal laboratory results, the overdose is reported as a non-serious Event of Clinical Interest (ECI), using the terminology “accidental or intentional overdose without adverse effect.”

All reports of overdose with and without an adverse event must be reported by the investigator within 24 hours to the Sponsor either by electronic media or paper. Electronic reporting procedures can be found in the EDC data entry guidelines. Paper reporting procedures can be found in the Investigator Trial File Binder (or equivalent).

